5.1 Schedule of Events

Table 3. Screening and study procedures to be done through the end of the study. Evaluation visit samples or activities should occur within 3 days of the scheduled study day

	Screening	Cycle 1					Monthly (until Month 6)	End of treatment
	Day <21	Day 1	Day 8 ±3days	Day 15 ±3days	Day 22 ±3days	Day 1 ±3days		
Informed Consent	X							
History and Demographics	X							
Hematological disorder diagnosis and prior therapy	X							
Urine HCG	X							
Vital Signs, ECOG PS and Physical Examination	X	X	X	X	X	X	X	
Concomitant medications	X	X	X	X	X	X	X	

Randomization	X						
CBC*	X	X	X	X	X	X	X
Fibrinogen	X						
Comprehensive metabolic panel**	X	X	X	X	X	X	X
Patient's questionnaire QOL		X					X
Transfusions records		X	X	X	X	X	X
Diary card***		X	X	X	X	X	X
Bleeding score WHO*	X	X	X	X	X	X	X
AE's		X	X	X	X	X	X
SAE		X	X	X	X	X	X

*First 30 days , i.e.: twice weekly or at the discretion of the treating physician, but at least once a week.(If the decision is twice a week, the non-visit day bleeding score may be assessed in person or by phone). After 30 days CBC and bleeding score will be performed according to the standard of care for cytopenic patients **glucose, serum calcium, blood urea nitrogen, creatinine, sodium, potassium, chloride, serum albumin, serum total proteins, carbon dioxide, alkaline phosphatase, aspartate amino transferase and alanine amino transferase. The screening procedures including blood and urine test obtained as part of the routine care, up to 72 hours prior to consenting, may be used to qualify the subject for eligibility and randomization. *** Diary card to be completed by Arm B - EACA

The following describes the procedures/tests required for this study:

Informed Consent: All patients must take part in the informed consent process prior to any study related activity. During the consent process, the person obtaining consent must inform the patient of all elements of informed consent. Adequate time must be allowed for questions and for the patient to make a voluntary decision. No protocol-specific procedures are to be performed until the patient has signed and dated the IRB approved informed consent form. Each patient's participation in the trial begins with the signing and dating of the informed consent form.

Screening: Screening tests and procedures are used to establish eligibility of the patient for the trial. Patients must continue to maintain laboratory values within eligibility parameters if any given procedure or laboratory test is repeated prior to randomization. All screening tests must be done within 7 days prior to randomization.

Randomization: Randomization procedure will be performed following complete eligibility assessments and just prior to the initiation of assigned treatment.

Medical/Surgical History and Demographics: Medical and surgical history and demographic information will be recorded. Medical and surgical history includes diagnoses, therapies, medical and surgical treatments, and current medications. Demographic information consists of the patient's age, gender, race, and ethnicity.

Hematological Disorder Diagnosis: The initial hematological diagnosis including the date of onset of the diagnosis must be recorded.

Vital signs and Physical Examination: Vital signs are temperature, pulse, respiratory rate, and blood pressure. A complete physical examination, including weight, must be performed at screening, prior to the first administration of study drug, and at the End-of-Treatment Visit. All subsequent physical examinations are part of the standard of care but should be directed to relevant bleeding findings in the patient.

Complete Blood Count (CBC): CBC with differential is defined as peripheral blood total white blood cell (WBC) count, hemoglobin, hematocrit, and platelet count. This is a standard of care test obtained routinely in all patients with hematological disorders.

Chemistry (Comprehensive metabolic panel): is a set of 14 chemical test including sodium, potassium, chloride, bicarbonate, blood urea nitrogen, creatinine, glucose, serum calcium, serum albumin, serum total proteins, carbon dioxide, alkaline phosphatase, aspartate amino transferase and alanine amino transferase

EQ-5D Assessments: The EQ-5D-5L will be used to collect patient-assessed quality of life and health outcomes measures. Patients are required to complete the instruments if there is a validated translation in a language in which they are fluent.

Bleeding score: Bleeding will be graded according with the WHO bleeding scale (Appendix 1) and recorded in the medical records during each visit. For hospitalized subjects enrolled on this trial, bleeding will be described in the daily follow up note by physician, nurse practitioner or physician assistant and graded by the investigator.

End of Treatment or Early Termination Procedures: The End-of-Treatment (or early termination) Visit should be performed within 2 weeks (14 days) of the patient's last dose of study drug or the patient/investigator decision to end treatment, whichever is later.

Follow-up Procedures: Safety: All AEs ongoing or starting within 30 days after the End-of-Treatment must be recorded on the CRF. After this time, ongoing AEs thought to be at least possibly study-drug related and all ongoing SAEs should be followed at least every 4 weeks until they resolve to baseline (or CTCAE grade ≤ 1), stabilize, or are considered to be chronic or irreversible.

Follow-up Procedures: Survival: Survival data will be collected every 12 weeks \pm 2 weeks starting after the last dose of the assigned study treatment or the investigator/patient decision to discontinue treatment, whichever occurs later and continuing for up to 12 months from the time the last patient is randomized to a treatment group. These data do not need to be obtained during a visit; phone contact is acceptable.

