Prohibited Medications/treatment	Hydroxyurea and procoagulant agents including DDAVP, recombinant FVII or prothrombin complex concentrate are prohibited in patients receiving EACA
Safety Evaluations	Clinical assessment once weekly during the first 30 days and then monthly for 6 months, CBC and bleeding score twice weekly the first 30 days, and then according to standard of care or at discretion of treating physician.
Statistical Analysis	
Population Analysis
 
Intention to treat (ITT) population: The ITT population includes all patients who are randomized to the study. Patients will be stratified and analyzed according to the treatment to which they were assigned.
 
Safety Population: The safety population includes all patients who have received at least 1 dose of EACA. Patients included in the safety population will be analyzed according to the treatment they received.
 
Per-protocol Population: The per-protocol population includes all patients who are randomized, receive at least one dose of study drug, and have no major protocol violations that could be expected to impact response data.
 
Study Endpoints

- **Primary Endpoint:** is to compare at the end of the study, the proportion of patients with major bleeding during the study period among patients randomized to receive either EACA or standard of care prophylactic platelet transfusions.
- **Secondary Endpoints** include:
 - proportion of patients with any bleeding during the study period in each arm
 - the total number of units of platelets transfused in each arm at the end of the study
 - Quality of life as measured in each arm before the study and at the end of the study
 - Safety in each arm

Sample Size

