The primary objective of this study is to compare the proportion of patients who develop major bleeding episodes (WHO grades 3-4) in the group randomized to receive prophylactic EACA versus standard of care prophylactic platelet transfusions.

2.2 Secondary Objectives:

- To compare the proportion of patients who develop any bleeding episode in the group randomized to receive prophylactic EACA versus standard of care prophylactic platelet transfusions.
- To compare, according to treatment with prophylactic EACA or prophylactic platelet transfusions, the total number of units of platelet transfused
- To compare the quality of life in both arms of the study

2.3 Hypothesis:

This is a non-inferiority trial in which we hypothesize that in thrombocytopenic patients with hematological malignancies, comparable incidence of bleeding will be observed with the prophylactic use of EACA and standard of care arm prophylactic platelet transfusions.

3 Investigational Plan

3.1 Overall Study Design and Plan:

This is a single center, randomized phase 2, open label trial of oral EACA versus platelet transfusions for the prevention of bleeding in thrombocytopenic patients with hematological malignancies.

Eligible patients with acute or chronic thrombocytopenia will be randomized in a 1:1 fashion to receive oral EACA at the dose of 1,000 mg twice daily as a substitute for prophylactic platelet transfusions or standard of care prophylactic platelet transfusions for an untransfused platelet count $< 20 \times 10^9/L$ in the out-patient or in the in-patient setting. Patients will be assessed twice weekly and as needed in between visits for the presence of bleeding. The number of platelets transfused for prophylaxis (arm B) or for therapeutic purposes (both arms) will be monitored. Patients will complete quality of life questionnaire. Adverse events will be assessed and graded according to the National Cancer Institute Common Terminology Criteria for Adverse Events (CTCAE) version 4.0. Bleeding will be assessed and graded according to the World Health Organization (WHO) classification [Appendix 1]. Patients will be assessed according to a protocol-specific schedule of events. Patients will continue treatment on trial until one or more criteria for discontinuation are met. Patients will be supplied with study drug until they discontinue from the study. Patients will be followed for 2 years or death, whichever occurs first.

3.2. Primary Endpoint:

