The primary endpoint is to compare the proportion of patients who develop major bleeding (WHO grade 3 or 4) in each arm.

3.3. Secondary Endpoints:

[figure not shown]
Secondary endpoints include:

- The proportion of patients who develop any bleed in each arm
- The total number of units of platelets transfused in each arm during the study period
- Quality of life as measured by EQ-5D-5L in each arm prior to start treatment and at the end of the study
- Safety in each arm

3.4. Description of Treatment:

Patients will be stratified by expected duration of thrombocytopenia (acute versus chronic), and randomized to receive oral EACA at the dose of 1,000 mg twice daily or the infusion of 1 U of single donor apheresis of platelet when untransfused platelet counts are $< 20 \times 10^9/L$ in the out-patient or $< 10 \times 10^9/L$ in the in-patient, as measured on at least twice weekly CBCs (standard of care for cytopenic patients). Schema of the trial is listed in Figure 3.

Study Schema.

3.5. Randomization:

Patients will be randomized on a 1:1 ratio within each strata (acute vs. chronic) to EACA (Arm B) or standard prophylactic platelet transfusions (Arm A) using a standard randomization table. The study is unblinded.

4. Patient Selection:

4.1. Inclusion Criteria:

- Age > 18 with a hematological malignancy
- Informed consent
- Thrombocytopenia with untransfused platelet counts < 20 x 10⁹/L in the out-patient or in the in-patient setting and one of the following criteria:
 1. Acute thrombocytopenia in patients with hematological malignancies who are in remission and are receiving myelosuppressive consolidation chemotherapy that is expected to induce marrow aplasia for at least 2 weeks; or
 2. Acute or chronic thrombocytopenia in patients with acute leukemia (myeloblastic or lymphoblastic) receiving induction or re-induction chemotherapy that is expected to induce marrow aplasia for at least 2 weeks; or Expected chronic thrombocytopenia in patients with newly diagnosed marrow failure syndromes, myelodysplastic syndromes, aplastic anemia, chronic myelomonocytic leukemia or myelofibrosis; or
 3. Expected chronic thrombocytopenia in patients with relapsed or refractory hematological malignancies; or

4. Hematopoietic stem cell transplant recipients with chronic thrombocytopenia due to chronic GVHD or other causes.

4.2 Exclusion Criteria:

- Acute promyelocytic leukemia
- Patient receiving anticoagulation
- Patient receiving antiplatelet agents

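### The protocol states the bleeding-score frequency in ways that disagree and lets an unblinded physician reduce it, so recording of minor bleeds is open to imbalance between arms

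*Protocol*

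**What the plan says.** Four places in the current Protocol bear on how often bleeding is looked for.

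- **Section 3.1:** "Patients will be assessed twice weekly and as needed in between visits for the presence of bleeding". No end date is given and no discretion to do less.
- **Synopsis, Safety Evaluations:** "CBC and bleeding score twice weekly the first 30 days, and then according to standard of care or at discretion of treating physician".
- **Section 5.1, Table 3 footnote (CBC and bleeding score together):** in the first 30 days, "twice weekly or at the discretion of the treating physician, but at least once a week". If twice weekly is chosen, "the non-visit day bleeding score may be assessed in person or by phone". Later, "After 30 days CBC and bleeding score will be performed according to the standard of care for cytopenic patients".
- **Section 3.4:** describes CBCs at least twice a week as the standard of care for cytopenic patients.

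Section 5.1 (Bleeding score) says the grade is "recorded in the medical records during each visit". For inpatients, "bleeding will be described in the daily follow up note by physician, nurse practitioner or physician assistant and graded by the investigator". Section 3.5 states: "The study is unblinded". Section 6.3.1.2 has prophylactic platelets given in the infusion center, while EACA is self-administered (Section 6.3). The diary card is for the EACA arm only and is described as a record of dosing dates (Section 6.3.1.1).

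The proportion of patients with any bleed is a secondary endpoint (Sections 3.3 and 8.3.2). Section 8.5.3 also plans a one-sided t-test on the number of bleeding episodes.

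**The concern.** The frequency statements cannot all be followed. The loosest one hands the choice to a physician who knows the arm.

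Scores are tied to visits, and one arm has a type of visit that the other lacks. Contact, and with it the number of looks, could therefore differ by arm. Short grade 1-2 bleeds are the ones most easily missed between looks, and they make up most of what is counted: in Table 2 of the Protocol, 27 of the 29 listed episodes are grade 1 or 2.

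Fewer looks in the EACA arm would record fewer minor bleeds there, in the direction of the one-sided test. Scores that were never taken cannot be restored in the analysis, so this belongs to trial conduct and not to an analysis plan.

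**Working it through.** **1. The statements side by side**

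| Source | First 30 days | After 30 days |
|---|---|---|
| Section 3.1 | twice weekly, plus as needed | the same, no limit |
| Synopsis | twice weekly | standard of care or discretion |
| Table 3 footnote | twice weekly or discretion, minimum weekly | standard of care |
| Section 3.4 (CBC only) | at least twice weekly | at least twice weekly |

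The footnote's weekly minimum conflicts with the other three rows. After 30 days, the footnote agrees with Section 3.1 if standard of care is read through Section 3.4. The synopsis still allows discretion.

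**2. Permitted number of scores**

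- First 30 days: 2 × 30/7 = 8.6 if twice weekly, and 30/7 = 4.3 at the weekly minimum.
- Whole period, with a month of 28 days (Section 8.1), 6 × 28 = 168 days = 24 weeks: 2 × 24 = 48 if twice weekly throughout. On the loosest reading, with four scores in cycle 1 and then only the monthly Table 3 visits, it is 4 + 5 = 9.

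**3. The plan's own figure**

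The design figure for the primary endpoint reproduces. Exact one-sided Fisher power at 45 per arm for 8% v 30% is 80.05%, and 45/0.90 = 50. It does not bear on this point.

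**4. Illustration**

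The following assumptions are not in the documents: each bleed is visible for 3 days, there is one bleed per patient on average over 168 days, there is no true difference, and there is no recall between scores. The platelet arm is scored every 3.5 days and the EACA arm every 7 days for as long as the gap lasts.

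- Detection = min(1, duration/interval): 3/3.5 = 0.857 and 3/7 = 0.429.
- P(any recorded bleed) = 1 − exp(−rate × detection).
- Rejection probability: one-sided 5% Fisher test, 50 per arm, by full enumeration.

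| Scenario | Platelet arm | EACA arm | Test favours EACA |
|---|---|---|---|
| Equal, twice weekly in both arms | 57.6% | 57.6% | 3.0% |
| Gap in first 30 days, both twice weekly after | 57.6% | 54.2% | 6.0% |
| Gap in first 30 days, both weekly after | 39.7% | 34.9% | 8.8% |
| Half the full gap in detection | 57.6% | 47.4% | 19% |
| Gap for all 168 days | 57.6% | 34.9% | 65% |

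For the second row, mean EACA detection is (30/168) × 0.429 + (138/168) × 0.857 = 0.781, and 1 − exp(−0.781) = 54.2%. If half the gap is taken on the recorded proportions instead (46.2%), the fourth row becomes 22%.

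**5. Sensitivity**

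Keep the full-period gap, let the true any-bleeding risk run from 41% (the 18/44 in Table 2) to 80%, and let bleeds be visible for 1 to 3 days. Recorded proportions then differ by 7 to 25 points, and the test favours EACA 19% to 78% of the time. If instead bleeds are visible or recalled for 7 days, detection is 1 under both intervals and the rate returns to 3.3%.

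**The case against.** The strongest reply is that the written rule is the same for both arms and that no section sets a different frequency by arm. That stands, and several further points do too.

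- EACA patients also need counts. Table 3 requires a CBC in both arms, and Section 5.3 ends treatment on two untransfused counts in either arm. Only the transfusion visits are specific to one arm.
- Section 3.4 supports reading standard of care as at least twice weekly, which would confine the gap mainly to the first 30 days.
- Inpatients have bleeding described daily. Section 3.1 adds as-needed assessment, and phone scoring rests on what the patient reports. Therapeutic platelets for grade ≥ 2 bleeds (Section 6.3.1.3) leave a transfusion record.
- The direction is plausible but not certain. A physician withholding prophylactic platelets might watch EACA patients more closely.
- The illustration uses a Fisher test on proportions, while Section 8.5.3 names a t-test on episode counts.

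A reader might infer that the any-bleeding comparison is biased, or that platelet-arm patients are bound to be scored more often. The documents support neither. Imbalance arises only if discretion or contact differs by arm in practice.

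The reply does not remove the contradiction. Section 3.4 speaks of CBCs and not of bleeding scores, the footnote itself allows weekly CBCs and scores, and the synopsis keeps discretion after day 30.

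**Conclusion.** The point holds as an inconsistency in the protocol that leaves minor-bleed ascertainment open to imbalance in an open-label trial. It is not a demonstrated bias.

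Its size cannot be derived from the documents. Under the base assumptions above, the false-positive rate runs from about 6% (gap confined to 30 days, twice weekly afterwards) to about 65% (gap over all 168 days), against 3% with equal schedules. The upper figure needs the physician to keep the EACA arm at weekly and the platelet arm at twice weekly for six months. It is an outer case, not an expectation.

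It would be tempting to extend the point to the primary endpoint. That is not supported to the same degree: under Appendix 1, grade 3-4 bleeds involve gross or debilitating loss, including any that requires red cell transfusion, and are much less likely to pass unnoticed between scores. The exposure is to the secondary any-bleeding and episode-count comparisons. The change is worth making because it is cheap and the lost information cannot be recovered later.

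**What to change.** Reconcile the synopsis, Sections 3.1 and 3.4 and the Table 3 footnote so that one minimum bleeding-score interval applies to both arms for the whole treatment period. The investigator chooses the interval; the point is that it is single and binding.

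- State the bleeding-score interval on its own, instead of deferring to standard of care or sharing a footnote with the CBC.
- Remove discretion to score less often than the minimum. Extra scores as needed can stay.
- Keep the phone option for non-visit days, which Table 3 already allows.
- Record and report the number of bleeding scores per patient by arm, so that any imbalance can be seen.

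The cost is amendment wording and some phone calls.

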5.2 Patient Registration and Identification

Demographic information on all patients who sign the Informed Consent Form will be recorded on the master subject log. Those patients who complete screening procedures and meet all eligible criteria may be enrolled. At the time of enrollment, the patient will be assigned a unique identification code (number), consisting of a study site number and a unique consecutive number.

5.2.1 Screen Failure

Patients who have signed informed consent and subsequently fail to meet the inclusion and/or exclusion criteria are defined as screen failures. For all screen failures, the Investigator is to maintain a screening log that documents the patient initials and reason(s) for screen failure. A copy of the log will be retained in the Investigator's study files. Any patient who is rescreened after screen failure must, in addition to the failed procedure, repeat only those screening procedures outlined in the Schedule of Events that have fallen outside the specified screening period.

5.2.2 Early Discontinuation

In the event that a patient is withdrawn from the study, every effort will be made by the Investigator to document and report the reasons for withdrawal as thoroughly as possible. The reason(s) for termination must be clearly reported on the appropriate page of the patient's CRF. An End-of-Treatment reason for discontinuation must be recorded for any patient who is randomized. If a patient is discontinued from the trial for any reason, every effort must be made to perform all clinical and laboratory procedures as scheduled for the End-of-Treatment Visit. In the event that the patient fails to return for the necessary visit(s), an effort must be made to contact the patient to determine the reason, and this information should be recorded in the appropriate source record and the end-of-treatment CRF.

5.3 Study Duration and End of Treatment

The total estimated duration of the study is up to 3 year, including 14 months to accrue patients with up to 1 year for treatment and follow up for the last patient. Patients will be supplied study drug until they discontinue from the study.

End of treatment is defined when untransfused platelet count recover to $> 30 \times 10^9/L$ on 2 measurements obtained 5 days apart. For patients without platelets recovery, end of treatment will be set at 6 months. At that time patients will be taken off treatment and enter a long-term follow-up period for 2 years.

Subjects that completed treatment due to platelet count recover to $> 30 \times 10^9/L$ on 2 measurements obtained 5 days apart whom developed thrombocytopenia > 30 days of end of study and fulfill the inclusions and exclusion criteria are allowed to be re-enrolled in the study. Subjects without platelet recovery that completed 6 months of treatment are not allowed to be re-enrolled in the study

